5.2.3.3 Prohibited Therapy

The following are prohibited medications during the study:

- All biologic therapy with a potential therapeutic impact on the disease being studied including but not limited to the following:
 - Etanercept (Enbrel®);
 - Infliximab (Remicade®);
 - Abatacept (Orencia®);
 - Anakinra (Kineret®);
 - Rituximab (Rituxan®);
 - Natalizumab (Tysabri®);
 - Tocilizumab (Actemra®);
 - Golimumab (Simponi®);
 - Certolizumab pegol (Cimzia®);
 - Ustekinumab (Stelara®);
 - Belimumab (Benlysta®);

- Vedolizumab (Entyvio®).
- Anti-IL-17 agents (Secukinumab, Ixekizumab, Brodalumab), including 28 days prior to Baseline and during the study.
- GMA, including 28 days prior to Baseline and during the study.
- Live vaccines, during the study and for 70 days after the last dose of study drug.
- Tofacitinib (Xeljanz®).
- Recreational or medical marijuana use 14 days prior to Baseline and during the study.
- Intravenous corticosteroid use or topical "Strongest" corticosteroid in Japanese Classification is prohibited within 14 days prior to Baseline and during the study.
- Investigational drugs of a chemical or biologic nature or investigational procedures are prohibited within 28 days or 5 half-lives (whichever is longer) of the drug prior to Baseline and during the study.

The AbbVie SDP identified in Section 6.1.5 should be contacted if there are any questions regarding prohibited therapy.

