5.2.2 Exclusion Criteria

1. Subject has erythrodermic psoriasis, guttate psoriasis, or subcorneal pustular dermatosis at Screening.
2. Subject diagnosed drug-induced GPP.
3. Total score of 14 or more in JDA severity index of GPP in GPP Medical Care Guideline 2014 in Japan.
4. Subject has other active skin disease (e.g., urticarial, atopic dermatitis) or skin infections (bacterial, fungal, or viral) that may interfere with evaluation of GPP, with the exception of footpad trichophytosis (athlete's foot).
5. Subject who cannot taper off cyclosporine until Week 8 after the Baseline and during the study. Subjects who cannot taper etretinate to 20 mg/day at the maximum dose prior to the Baseline.
6. Subject who is receiving oral corticosteroid more than 10 mg/day at the Baseline, and cannot taper off until Week 4 after the Baseline and during study.
7. Subject who received granulocyte and monocyte adsorption apheresis (GMA) therapy for at least 28 days prior to the Baseline and cannot avoid this therapy during the study.
8. Subjects who received any investigational agents of chemical or biologic nature (including anti-IL17 agents), which would be efficacious to GPP or psoriasis-related skin disease for at least 28 days or 5 half-lives of the drug prior to the Baseline, whichever is longer, and during the study.
9. Subjects who received ustekinumab for at least 84 days prior to the Baseline and during the study.
10. Subject who cannot avoid PUVA or narrow-band UVB phototherapy for at least 14 days prior to the Baseline and during the study.
11. Subject who cannot avoid "Strongest" corticosteroid in Japanese classification of topical therapy for at least 14 days prior to the Baseline and during the study.

12. Subject who cannot avoid anti-tumor necrosis factor (TNF) agent other than infliximab and adalimumab (including but not limited to etanercept [Enbrel], golimumab [Simponi] or certolizumab pegol [Cimzia]) for at least 28 days prior to the Baseline and during the study.
13. Prior exposure to adalimumab.
14. Subject who has previous used infliximab:
 - and has not clinically responded at any time ("primary non-responder") unless subject experienced a treatment limiting reaction, or
 - who used infliximab ("secondary treatment failure") within 42 days prior to the Baseline.

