1, 2	To avoid medical conditions that may compromise the ability to identify subjects with the correct diagnosis or to interpret medical importance of clinical results
3, 18, 21	To exclude subjects who maybe at increased risk for protocol non-adherence or premature discontinue
4 – 15	To avoid bias for the evaluation of efficacy and safety by concomitant or prior use of other medications or treatments

16, 17, 19, 20, To reduce the risk to subjects or others and/or to exclude underlying
22 – 28 conditions that would compromise the subject's safety

29 To maintain the integrity of other aspects of study conduct, including,
subject sampling, treatment procedures, etc.

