5.2.3.2 Concomitant Therapy

Doses of etretinate (tapered to 20 mg/day at maximum dose prior to the Baseline), MTX, azathioprine, or salazosulfapyridine taken at Baseline will be continued and remain stable throughout the study. Doses may be decreased or terminated in the event of moderate-to-severe treatment-related toxicities or improvement of GPP skin lesion according to the discretion of the investigator. Dose escalation of these treatments will not be allowed.

Doses of topical corticosteroids ("Very strong," "Strong," "Medium" and "Weak" in Japanese classification), topical vitamin D3, or topical tacrolimus taken at the Baseline will be continued without dose escalation. Dose escalation (increase of amount for use) of topical corticosteroids is allowed only to use lower classes of drugs. Doses may be decreased or terminated in the event of moderate-to-severe treatment-related toxicities or improvement of GPP skin lesion according to the discretion of the investigator.

For subjects who are on oral steroids at the Baseline, their steroid dose must be tapered off for 4 weeks (until Week 4) and withdrawn for the rest of the study period. For subjects

who are on cyclosporine at the Baseline, the treatment must be tapered off for 8 weeks (until Week 8) and withdrawn for the rest of the study period.

Changes in all concomitant medications will be assessed at each study visit from Baseline (Week 0) through Week 52/PD Visits. Any changes will be documented, including the reason for the change of dose will be documented in the source documents and captured on the appropriate eCRF page.

Prophylaxis treatment with isoniazid for TB will be recorded. Even if a subject prematurely discontinues the study, isoniazid treatment should be continued for 9 months considering the best interest of the subject at the discretion of the investigator.

Any vaccine (except for live vaccines) administered during the study will be recorded in the eCRF as a concomitant medication.

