5.3.4 Pharmacokinetic Variables

Pharmacokinetic

Serum concentrations of adalimumab at each scheduled sampling time will be reported. Changes in serum adalimumab concentration in subjects who get dose-escalated will also be reported.

Immunogenicity

The number and percentage of subjects who develop AAA will be determined.

5.4 Removal of Subjects from Therapy or Assessment**5.4.1 Discontinuation of Individual Subjects**

A subject may withdraw from the study at any time. The Investigator may discontinue any subject's participation for any reason, including an adverse event, safety concerns or failure to comply with the protocol.

Subjects will be withdrawn from the study immediately if any one of the following occurs:

- Clinically significant abnormal laboratory result(s) or adverse event(s), as determined by the Investigator in consultation with the AbbVie SDP.
- The Investigator believes it is in the best interest of the subject.
- The subject requests withdrawal from the study.
- Inclusion and exclusion criteria violation was noted after the subject started study drug, when continuation of the study drug would place the subject at risk as determined by the AbbVie SDP (Section 5.2 and Section 7.0).
- Introduction of prohibited medications or dosages when continuation of the study drug would place the subject at risk as determined by the AbbVie SDP.
- Subject is non-compliant with TB prophylaxis.
- The subject becomes pregnant while on study medication.
- Subject has dysplasia of the gastrointestinal tract or a malignancy, except for localized non-melanoma skin cancer. Discontinuation for carcinoma in situ of the cervix is at the discretion of the Investigator.
- Subject is diagnosed with lupus-like syndrome, multiple sclerosis or demyelinating disease.
- Subject is significantly non-compliant with study procedures which would put the subject at risk for continued participation in the trial, as determined by the Investigator, in consultation with the AbbVie SDP.

If, during the course of study drug administration, the subject prematurely discontinues study drug use, the procedures outlined for the PD Visit must be completed within

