7.0 Protocol Deviations

AbbVie does not allow intentional/prospective deviations from the protocol. The principal investigator is responsible for complying with all protocol requirements, and applicable global and local laws regarding protocol deviations.

For the purposes of the protocol, reportable deviations are defined as:

- Subject entered into the study even though she/he did not satisfy entry criteria
- Subject who developed withdrawal criteria during the study and was not withdrawn
- Subject who received wrong treatment or incorrect dose
- Subject who received excluded or prohibited concomitant treatment

If a protocol deviation occurs (or is identified) after a subject has been enrolled, the principal investigator is responsible for notifying IEC/Institutional Review Board (IRB), regulatory authorities (if appropriate), and the following AbbVie Clinical Monitor(s):

Primary Contact:

Alternate Contact:

Such contact must be made as soon as possible to permit a review by AbbVie to determine the impact of the deviation on the subject and/or the study.

The Investigator will record all protocol deviations in the appropriate medical records at site.

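### No planned analysis counts as a non-responder a subject who begins or increases another GPP-active treatment before the Week 16 assessment and has a score in the window

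*Protocol*

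**What the plan says.** **Treatment rules.** Protocol 5.2.3.3 begins "The following are prohibited medications during the study". The list covers biologics with a potential effect on GPP (infliximab by name), anti-IL-17 agents, GMA, tofacitinib, intravenous and topical strongest-class corticosteroid, and investigational drugs. It does not name cyclosporine, oral corticosteroid, etretinate, MTX, azathioprine or salazosulfapyridine.

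Protocol 5.2.3.2 covers those drugs for subjects already taking them. The cyclosporine rule addresses those "who are on cyclosporine at the Baseline, the treatment must be tapered off for 8 weeks (until Week 8) and withdrawn"; oral steroid must likewise be off by Week 4, and neither may resume. "Doses of etretinate (tapered to 20 mg/day at maximum dose prior to the Baseline), MTX, azathioprine, or salazosulfapyridine taken at Baseline will be continued" at a stable or reduced dose, without escalation.

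The exclusion criteria (5.2.2) show the intent. Exclusion 5 reads "Subject who cannot taper off cyclosporine until Week 8 after the Baseline and during the study". Exclusion 10 reads "Subject who cannot avoid PUVA or narrow-band UVB phototherapy for at least 14 days prior to the Baseline and during the study". The rationale for exclusions 4 to 15 is "To avoid bias for the evaluation of efficacy and safety by concomitant or prior use of other medications or treatments".

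**Consequences for conduct.** Protocol 7.0 makes "Subject who received excluded or prohibited concomitant treatment" a reportable deviation. Protocol 5.4.1 requires withdrawal for "Introduction of prohibited medications or dosages when continuation of the study drug would place the subject at risk as determined by the AbbVie SDP", so not in every case. Protocol 6.3, on toxicity management, lets otherwise prohibited drugs be given when medically necessary and foresees restarting adalimumab afterwards.

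**Analysis.** SAP 10.2 applies non-responder imputation (NRI) to missing data, and SAP 6.5 defines it for missing values alone and adds an observed-case analysis. SAP 6.4 sets the Week 16 window at Days 100–141 (target Day 113), uses the visit closest to target, and maps early-termination visits to windows.

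**The concern.** The trial has one arm and ten subjects, and Protocol 3.0 describes etretinate, cyclosporine and infliximab as effective in GPP. If a subject does poorly on adalimumab, receives one of these drugs and improves by Week 16, no control arm offsets the gain. The analysis credits the response to adalimumab.

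The SAP is strict with subjects who leave, since a missing Week 16 value is a failure. It has no counterpart for subjects who stay and receive additional treatment. At stake is whether the headline rate can be read as response to adalimumab without added GPP-active treatment.

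**Working it through.** **1. The plan's own figures.** Inputs from Protocol 8.2: n = 10, threshold p0 = 0.10, expected p1 = 0.50, one-sided 0.025.

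- Chi-square power = Φ[(√n(p1 − p0) − 1.96√(p0(1 − p0))) / √(p1(1 − p1))] = Φ[(1.265 − 0.588)/0.5] = Φ(1.354) = 91.2%, as stated.
- Exact binomial: P(X ≥ 3 | 0.10) = 0.070 and P(X ≥ 4 | 0.10) = 0.0128, so the boundary is 4 of 10. P(X ≥ 4 | 0.50) = 82.8%; the plan states 82%.

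These figures are sound. They are used here only to locate the 10% benchmark.

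**2. Three subjects traced through the rules.**

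| Subject | Rule | Week 16 status |
|---|---|---|
| Stops early, no assessment in Days 100–141 | SAP 6.5, 10.2 | Missing, so non-responder |
| Stays on adalimumab, starts cyclosporine at (say) Week 10, attends Week 16 | Protocol 5.4.1 does not force withdrawal; value observed | Scored on the observed value |
| Stops adalimumab, starts another drug, has a premature discontinuation (PD) visit in Days 100–141 | Protocol 5.4.1; SAP 6.4 | Scored on the observed value, if that visit is closest to Day 113 |

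The third route is narrow. The PD visit is due within 2 weeks of the last dose, so an on-time visit on Day 100 needs a last dose on Day 100 − 14 = Day 86 or later. Protocol 5.4.1 prefers that visit to come before any new therapy but does not require it. A drug begun after the last dose would have at most about 14 days to act.

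**3. Does any other planned output close the gap?** The observed-case analysis keeps observed scores. SAP 10.3 tabulates the proportion taking systemic co-medication by visit, SAP 7.3 counts medications, and SAP 8.0 summarises deviations; none is tied to response. The Clinical Response subgroups in SAP 10.5 are dose escalation and prior infliximab. So none does.

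**4. Size per subject (Clopper-Pearson 95% CI, n = 10).**

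| Responders | Rate | Exact 95% CI |
|---|---|---|
| 5 | 50% | 18.7% to 81.3% |
| 4 | 40% | 12.2% to 73.8% |
| 3 | 30% | 6.7% to 65.2% |

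One reclassified responder moves the rate by 1/10 = 10 points. From 4 to 3, the lower limit passes below 10%.

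**5. Illustration under an assumed frequency.** Let r be the chance that a subject who would not respond to adalimumab starts such a treatment and is scored a responder because of it. The documents give no value for r. With true rate p and independent subjects:

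- expected reported rate = p + (1 − p)r
- P(at least one such subject) = 1 − [1 − (1 − p)r]^10
- P(count lifted from ≤ 3 to ≥ 4) = Σ over k = 0 to 3 of C(10,k) p^k (1 − p)^(10 − k) × P(Bin(10 − k, r) ≥ 4 − k)

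For p = 0.50 and r = 0.05, the k = 3, 2 and 1 terms are 0.03535 + 0.00252 + 0.00008 = 0.03795, and k = 0 is negligible.

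| r | Reported rate, p = 50% | At least one, p = 50% | Lifted past 3, p = 50% | Lifted past 3, p = 60% |
|---|---|---|---|---|
| 0% | 50.0% | 0% | 0% | 0% |
| 5% | 52.5% | 22% | 3.8% | 1.3% |
| 10% | 55.0% | 40% | 7.0% | 2.4% |
| 20% | 60.0% | 65% | 11.7% | 3.9% |

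**The case against.** Scoring each subject's state at Week 16 whatever else was taken is a legitimate choice. Use of other drugs is also not hidden: the SAP adds oral steroids and cyclosporine to the protocol's co-medication table and plans medication and deviation summaries. New starts may be rare, because inclusion 4 selects subjects who failed, cannot tolerate or cannot take approved treatment, and dose escalation is available from Week 8. SAP 10.1 defines no significance level for efficacy and plans descriptive results, so no planned decision turns on 4 versus 3 responders.

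All of that stands, and it argues for leaving the primary analysis alone. It does not supply the missing figure. The tables would show that a drug was taken, but not what the response rate is when that subject is not counted as a success.

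A reader might also infer that the protocol leaves subjects free to start any systemic GPP drug. The documents do not support that. The classes listed in 5.2.3.3 are barred outright. Exclusion 10 read with 7.0 largely covers phototherapy. Exclusions 5 and 6, their rationale and the no-escalation rule show the intent for the conventional drugs. Sites are told to take questions on concomitant or prohibited therapy to the sponsor's physician. What remains is a clarity gap about a first start of a conventional systemic drug. Even that is conditional: SAP 3.0 follows a protocol dated 06 April 2017 with administrative changes 1 to 4, whereas the supplied synopsis is dated 08 June 2015, and the later text may list these drugs.

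**Conclusion.** The analysis gap holds and does not depend on how the prohibited list is worded. Even an outright prohibited drug does not by itself remove a subject or change a Week 16 score, and no planned analysis counts such a subject as a failure. The gap in the prohibited list is secondary and applies to the supplied text only.

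The firm size is 10 points per affected responder. Anything beyond that rests on r, which is assumed. With no new starts nothing changes, and at a true rate of 60% the chance of being lifted past three responders stays below 4% even at r = 20%. The 10% figure is the sample-size benchmark, not a success rule. A reader might infer that the Week 16 rate is inflated or that the primary analysis is wrong. The documents support neither; they show only that the plan could not reveal such inflation if it occurred. One supporting table before database lock is a proportionate response.

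**What to change.** Add to SAP 10.2, leaving the primary NRI analysis unchanged:

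> Sensitivity analysis (FAS): Week 16 Clinical Response with exact 95% CI, counting as a non-responder any subject who, after the first dose and up to the assessment used for Week 16 (including a premature discontinuation visit in Days 100–141), starts, restarts or increases systemic therapy for GPP (cyclosporine, oral or intravenous corticosteroid, etretinate, MTX, azathioprine, salazosulfapyridine, a prohibited biologic or GMA) or starts phototherapy for GPP. Protocol-specified tapers and courses with a recorded non-GPP indication are not counted. Each counted case is listed with drug, dates and Week 16 score.

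The listing lets a reader see when a case was only a brief early course, for which the rule is conservative.

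**Cost.** One table and one listing, with no extra visits, tests or data: Protocol 5.2.3.1, 5.2.3.2 and 10.1 already provide for dates, changes and reasons for treatment. The downside is a supporting rate that may be lower than the primary one.

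**Optional.** If the 06 April 2017 protocol does not already do so, add a bullet to 5.2.3.3 barring new starts of the conventional systemic drugs and of phototherapy for GPP. It should except the tapers and stable Baseline doses in 5.2.3.2 and be reconciled with the medically-necessary exception in 6.3. This needs an amendment and IRB approval, and helps only if subjects have yet to reach Week 16; the documents do not give enrolment status.

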5.3 Efficacy, Pharmacokinetic, and Safety Assessments/Variables

5.3.1 Efficacy and Safety Measurements Assessed and Flow Chart

Study procedures will be performed as summarized in Section 5.3.1.1. All subjects must meet the study selection criteria outlined in Section 5.2.1 and Section 5.2.2 in order to be enrolled into the study.

Table 1. Study Activities

Activity	Screening (Day -30 to Day -1)	Baseline ^a (Day 1)	Wk 2	Wk 4	Wk 8	Wk 12	Wk 16	Wk 20	Wk 24	Wk 28	Wk 32	Wk 36	Wk 40	Wk 44	Wk 48	Wk 52 or Premature Discontinuation Visit	Unscheduled Study Visit	70- Day Call
Informed Consent	X																	
Assign Subject ID Number	X																	
Subject Background	X																	
Inclusion/Exclusion Criteria	X	X ^b																
Medical/Surgical History	X	X ^b																
Prior and Concomitant Therapy Assessment	X	X ^b	X	X	X	X	X	X	X	X	X	X	X	X	X	X	X	
Alcohol Use	X																	
Tobacco Use	X																	
Physical Exam ^c	X	X	X	X	X	X	X	X	X	X	X	X	X	X	X	X	X	
Chest X-Ray/12-Lead ECG ^e	X															X ^f	X ^g	
TB Screening ^h	X																	
Vital Signs	X ⁱ	X	X	X	X	X	X	X	X	X	X	X	X	X	X	X	X	
Pregnancy Tests	X ^j	X ^k														X ^k		
General Labs ^l : Blood Chemistry and Hematology	X	X ^m	X	X	X	X	X	X	X	X	X	X	X	X	X	X ^s	X	

Table 1. Study Activities (Continued)

Activity	Screening (Day -30 to Day -1)	Baseline ^a (Day 1)	Wk 2	Wk 4	Wk 8	Wk 12	Wk 16	Wk 20	Wk 24	Wk 28	Wk 32	Wk 36	Wk 40	Wk 44	Wk 48	Wk 52 or Premature Discontinuation	Unscheduled Study Visit	70- Day Call
Urinalysis ⁿ	X	X														X		
HIV Screen ^o	X																	
Hepatitis B Screen ^p	X																	
Hepatitis C Screen	X																	
Antinuclear Antibody (ANA)/Anti-Double- Stranded DNA (dsDNA) ^q																		
Photography ^r	X	X	X	X	X	X	X	X	X	X	X	X	X	X	X	X		
GPP Skin Score and BSA, Systemic/Laboratory Score	X	X	X	X	X	X	X	X	X	X	X	X	X	X	X	X ^s		
PGA	X	X	X	X	X	X	X	X	X	X	X	X	X	X	X	X	X ^s	
PASI Score	X	X	X	X	X	X	X	X	X	X	X	X	X	X	X	X	X ^s	
DLQI		X														X		
SF-36		X														X		
Dispense Study Drug	X	X	X	X	X	X	X	X	X	X	X	X	X	X	X	X	X ^s	
Administer Study Drug ^t	X	X	X	X	X	X	X	X	X	X	X	X	X	X	X	X	X ^s	
PK Measurements ^u	X	X	X	X	X	X	X	X	X	X	X	X	X	X	X	X	X ^s	
AAA Measurements ^u	X	X	X	X	X	X	X	X	X	X	X	X	X	X	X	X	X ^s	

Table 1. Study Activities (Continued)

Activity	Screening (Day -30 to Day -1)	Baseline ^a (Day 1)	Wk 2	Wk 4	Wk 8	Wk 12	Wk 16	Wk 20	Wk 24	Wk 28	Wk 32	Wk 36	Wk 40	Wk 44	Wk 48	Wk 52 or Premature Discontinuation Visit	Unscheduled Study Visit	70- Day Call
Monitor Adverse Events ^v	X	X	X	X	X	X	X	X	X	X	X	X	X	X	X	X	X	
Follow-Up Phone Call																	X ^w	

Footnote for Table 1:

- a. The Baseline visit date will serve as the reference for all subsequent visits. A \pm 7-days window is permitted around scheduled study visits.
- b. Update inclusion/exclusion, medical/surgical history, and prior and concomitant therapy information to assure subject eligibility.
- c. Physical examinations performed at Screening, Week 24 and Week 52/PD Visits will be full physical examinations. Physical exams performed at all other visits will be symptom-based.
- d. Chest x-ray (CXR) includes posterior-anterior [PA] **and** lateral views. Subjects with normal chest x-ray within 90 days of Screening will not require a repeat chest x-ray, if documentation is available.
- e. Subjects with normal ECG within 90 days of Screening will not require a repeat ECG, if documentation is available.
- f. Subjects will have a repeat CXR or ECG at Week 52 or the appropriate Premature Discontinuation visit, only if in the opinion of the investigator, clinically significant AEs develop during the study that warrant a repeat.
- g. Subjects can have a repeat CXR/ECG at any time during the study as warranted based on the opinion of the Investigator.
- h. Subjects with negative latent TB test(s) (In case a subject received both a PPD test and IGRA, both must be negative) within 90 days of Screening will not require a repeat latent TB test, if documentation is available. PPD skin test is to be read 48 to 72 hours after placement.
- i. Height will be measured at the Screening only.
- j. All females of childbearing potential will have a serum pregnancy test at the Screening that is performed at the central laboratory.
- k. All females of childbearing potential will have a urine pregnancy test at the Baseline and Week 52 or Premature Discontinuation visits at the central laboratory. Any subject with a positive urine pregnancy test must have a negative serum test performed at the central laboratory prior to start of the treatment in the study. Urine pregnancy test at the Baseline will be performed also at site to confirm negative result on site. If the result at site is positive, treatment with study drug should not be started until the serum pregnancy test at the central laboratory is confirmed negative.
- l. Subject should be fasting. Please refer to the laboratory manual for further instructions.

Table 1. Study Activities (Continued)

- m. Laboratory assessments will only need to be repeated at the Baseline if the time between blood sampling for Screening and Baseline is greater than 14 days, or if the subject's health status has changed to warrant a repeat test.
- n. Dipstick urinalysis will be conducted by the central laboratory at all required study visits. A microscopic analysis will be performed in the event the dipstick results show protein, ketones or blood greater than negative or glucose greater than normal.
- o. Subjects will be tested for HIV and documented that the test has been performed. This testing is to be done at the central laboratory. A subject will not be eligible for study participation if test results indicate a positive HIV infection. AbbVie will not receive results from the testing and not be made aware of any positive result.
- p. Subjects will be tested for the presence of the Hepatitis B Virus (HBV) at Screening. A positive result for the hepatitis B surface antigen (HBs Ag) will be exclusionary. Samples that are negative for HBs Ag will be tested for surface antibodies (HBs Ab) and core antibodies (HBc Ab Total). Subjects with HBs Ag (-), HBs Ab (-), and HBc Ab Total (+) require PCR qualitative testing for HBV DNA. Any HBV DNA PCR result that meets or exceeds detection sensitivity will be exclusionary.
- q. Anti-dsDNA will be measured if ANA is positive.
- r. Photographs of skin lesion will be taken at the time points above in subjects who agree to do in the pre-selected sites.
- s. When dose escalation is decided on unscheduled visit or on any visit when the data collection is not planned, the investigator must assess skin lesion (GPP skin score, BSA, PGA and PASI score), and perform blood sampling for laboratory test and PK/AAA prior to dose escalation. Body temperature will come from Vital Signs. Additional study drug dispense may be necessary, if appropriate.
- t. Administration of study drug will be performed after all assessments and examinations scheduled for that day have been completed. Study drug will be administered every other week in the investigator's office or at subject's home after training of self-injection to ensure proper technique.
- u. Blood samples for the measurement of adalimumab and AAA concentrations will be collected prior to dosing.
- v. All AEs reported from the time of study drug administration until 70 days following discontinuation of study drug administration will be collected. SAEs and protocol-related nonserious AE will be collected from the time the subject signed the study-specific informed consent until 70 days following discontinuation of study drug administration.
- w. Site personnel will contact all subjects by phone 70 days after the last dose of study drug to determine the status of any ongoing AEs/SAEs or the occurrence of any new AE/SAEs.

